12.1 CRITERIA FOR THERAPEUTIC RESPONSE/OUTCOME ASSESSMENT

The primary objective of this study is to assess toxicity associated with combined LDR brachytherapy and hypofractionated radiation therapy for intermediate risk prostate cancer at 12 months via CTCAE v4.0. Both acute and late toxicity associated with radiation therapy will be evaluated in a fashion similar to those used in prior studies of radiation therapy in prostate cancer patients. All grade 2 or higher toxicities will be evaluated and attributed to radiation therapy or not. Evaluation will be carried out prior to treatment to serve as a baseline. During each subsequent followup visit, patients will be asked to complete questionnaires (IPSS, IIEF, and EPIC) and asked about symptoms. The primary expected toxicities are genitourinary and gastrointestinal (rectal). Sexual function assessment is included but is not considered an SAE.

The following instruments will be used in the evaluation of toxicities:

Appendix 1-NCI CTCAE v 4.0

Appendix 2-International Prostate Symptom Score

Appendix 3-International Index of Erectile Function-6

Appendix 4- EPIC urinary, bowel and sexual domain

a. NCI Common Toxicity Criteria. The NCI scales are simple to complete and provide a means for assessing patient symptoms. Only the CTCAE v 4.0 will be used in toxicity grading.

b. International prostate symptom score index (IPSS). This validated and widely used instrument is a patient administered questionnaire that is currently part of routine patient evaluation. The IPSS index is a seven item questionnaire designed to assess urinary functioning, specifically urinary frequency, nocturia, weak urinary stream, hesitancy, intermittence, incomplete emptying, and urgency. Questions are rated on a six point Likert scale with higher scores indicating more difficulty in urinary functioning. This measure demonstrated a high internal consistency (Cronbach's alpha = 0.84) with excellent test-retest reliability ($r = 0.92$). The IPSS index also demonstrated good validity with strong associations with other measures of urinary difficulties. The IPSS index also showed appropriate sensitivity to change. This measure has been widely used

in clinical practice and research protocols (See appendix 2). It will be used as part of pretreatment evaluation and in follow-up and will be summarized using descriptive statistics.

c. Sexual function will be assessed before treatment and at each follow up appointment with the International Index of Erectile Function (IIEF) (See appendix 3). The IIEF short form is a 6 item questionnaire which measures participants' responses on a 5 and 6 point Likert Scale. A principal components analysis identified five distinct factors (i.e., erectile function, orgasmic function, sexual desire, intercourse satisfaction, and overall sexual satisfaction). The IIEF demonstrated a high degree of internal consistency for the overall scale (Cronbach's alpha = 0.91) as well as the five factors (Cronbach's alpha values greater than 0.73). Test-retest reliability was also strong for the total score and the five domain scores. The IIEF demonstrated adequate construct validity, and all five domains showed a high degree of sensitivity and specificity to the effects of treatment. Significant (P values = 0.0001) changes between baseline and post-treatment scores were observed across all five domains in the treatment responder cohort as compared to the nonresponder cohort in the original validation study. This questionnaire takes approximately 3 minutes to complete.

d. EPIC is a 32 item questionnaire for patients with prostate cancer assessing urinary function, bowel habits, sexual function, hormonal function, and overall satisfaction. The grading scales vary per question (in some cases, a high score indicates more severe symptoms, but in others a lower score indicates worse symptoms).

We plan to use the assessment scores which are part of our standard followup to describe trends in scores over time. We plan to summarize and present all 14 scores for the EPIC at all 9 assessment times. Only the total scores from the IPSS and IIEF will be used. We will consider a clinically significant change if there is a change of 5 or more in the total score of the IPSS, IIEF, or EPIC questionnaires.

Post-treatment PSA relapse-free survival will be studied using serial PSA measurements after treatment as detailed above. PSA relapse free survival will be defined as the time from the end of radiation therapy to PSA relapse or last follow-up. PSA relapse will be defined according to the revised American Society for Therapeutic Radiology and Oncology consensus and Houston definition (absolute nadir plus 2ng/mL dated at the time of failure).

Post-treatment biopsy results will be analyzed using the current MSKCC institutional standard developed and published by the Departments of Pathology and Radiation Oncology. Specifically, pathologic response rates from biopsies will be divided into 3 categories:

- 1) Prostate adenocarcinoma without typical radiation-induced changes
- 2) Prostate adenocarcinoma with radiation-induced changes
- 3) No evidence of prostate adenocarcinoma

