4.1 OVERVIEW OF STUDY DESIGN/INTERVENTION

4.2 Design

Patients enrolled in this study will undergo LDR prostate brachytherapy followed approximately 4 weeks later with hypofractionated, image-guided intensity modulated radiation therapy to a dose of 25Gy in 5 fractions of 5Gy delivered every other day. Radiobiologically, as indicated in the BED calculations in Section 3, the dose of hypofractionated radiotherapy is expected to have less acute toxicity and equivalent late toxicity as standard fractionated treatment. Both brachytherapy and hypofractionated external beam radiation therapy will be delivered using the same equipment, techniques and treatment planning procedures as currently practiced at MSKCC.

Patients will be followed post-treatment at 1, 3, 6 (+/- 4 weeks) and every 6 months (+/- 4 weeks) thereafter until 36 months. During the post-treatment followup, patients will be evaluated for urinary, bowel/rectal, and sexual toxicity. Baseline measures of these domains will be obtained prior to treatment. The primary endpoint will be urinary toxicity as assessed by CTCAE v4.0 at 12 months. Bowel and sexual function will also be assessed at followup as

secondary endpoints. Serum PSA levels will be drawn on the same schedule as clinical followup. Post-treatment prostate biopsies will be obtained once at 24-36 months post-treatment to evaluate pathologic response to therapy.

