10.1 EVALUATION DURING TREATMENT/INTERVENTION

Patients who cannot meet the necessary dosimetric constraints will not be eligible for participation in the study and will be withdrawn from study, since they will already be enrolled at this time

- There will be at least one status check visit during the course of hypofractionated external beam radiotherapy.
- Participants will have clinic follow-up visits at 1, 3, and 6 months (+/- 4wks) posttreatment.
- Then at 6 month intervals (+/- 4wks) post treatment.
- Follow-up scheduling is based on the last day of hypofractionated treatment.
- At each followup visit, patients will undergo standard DRE and serum PSA. Patients will also be asked to complete sexual quality of life questionnaires (EPIC), and urinary and rectal quality of life questionnaires (IPSS and IIEF), which will be captured per standard of care and be assessed for toxicity using CTCAE 4.0. If patient is unable to come in for a followup appointment, a telephone followup will suffice and the PSA and DRE will be deferred. IPSS, IIEF, and EPIC questionnaires can be completed over the phone or sent to patients via mail, fax, or electronic mail by the physician or the physician's office assistant if the patient is unable to come in for a follow-up appointment. If the patient cannot be reached by phone or prefer to complete the questionnaires personally, the questionnaires will be sent via mail, fax or electronic mail. The questionnaires sent directly to patients must be blank forms with no patient identifiers, only study ID numbers. If questionnaires are sent via mail, the patient must be provided with a pre-filled business envelop that will allow patients to return it with no expense. Patients must also have the option of returning questionnaires by electronic mail or fax. If a patient is unable to come in for a follow-up appointment or complete the questionnaires over the phone, the method by which questionnaires are sent to patients and the method by which questionnaires are returned will be determined based on the patient's preference or if they are unable to be contacted by phone, the contact information on file for the patient as some patients may not have access to a phone, fax or electronic mail. A repeat prostate biopsy will be completed between months 24 and 36 for pathologic response assessment. This is a standard assessment tool.

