14.0 BIOSTATISTICS

The primary objective is to assess the toxicity of hypofractionated radiation therapy in combination with brachytherapy for the treatment of intermediate risk prostate cancer. To set up a decision rule we will focus on the CTCAE v 4.0 (see appendix) grade 2 or higher GU toxicity observed at the 1-year follow-up time (+/- 4 weeks). We will enroll 40 evaluable patients, and if 12 or more patients have a CTCAE v4.0 grade 2 or higher toxicity at 1 year, this treatment will be deemed too toxic and the study will be stopped. Otherwise it will be declared safe. This decision rule has the following probabilities of declaring treatment unsafe

True toxicity rate	0.15	0.20	0.25	0.30	0.35	0.40	0.45
Probability of declaring unsafe	1%	8%	28%	56%	79%	92.9%	98.2%

Patients who withdraw, die due to reasons other than toxicity, or fail to provide the 1-year CTCAE v4.0 GU toxicity status will be replaced by new patients. To this end we may need to enroll an additional 4 patients (10%).

For the secondary objectives, all toxicities will be tabulated by type and grade. Post-treatment PSA values will be summarized numerically and graphically. Time to PSA relapse will be analyzed by Kaplan-Meier estimation. The pathologic response rates at 24-36 months will be calculated as sample proportion based on the available patients and confidence intervals will be provided. Erectile function evaluated by IIEF will be summarized by descriptive statistics.

It is expected that it will take approximately 3 years to accrue the total of 45 patients.

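### PSA relapse-free time runs to last follow-up, which may be a telephone contact without a PSA; it should end at the last PSA (minor)

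*Combined protocol and SAP*

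**What the plan says.** Section 2.1 lists PSA relapse-free survival as a secondary objective. Section 12.1 gives the data source: "Post-treatment PSA relapse-free survival will be studied using serial PSA measurements after treatment as detailed above". It then gives the time scale: "PSA relapse free survival will be defined as the time from the end of radiation therapy to PSA relapse or last follow-up". The event follows the revised consensus definition, summarised as "absolute nadir plus 2ng/mL dated at the time of failure".

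On visits, Section 4.2 says "Serum PSA levels will be drawn on the same schedule as clinical followup", that is, at months 1, 3 and 6 and then every 6 months to month 36. Section 10.1 adds an exception: "If patient is unable to come in for a followup appointment, a telephone followup will suffice and the PSA and DRE will be deferred". It sets no date for the deferred draw and no limit on the number of telephone visits.

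On analysis, Section 14.0 says only "Time to PSA relapse will be analyzed by Kaplan-Meier estimation". It does not state a censoring date.

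**The concern.** Relapse can be seen only on a PSA result, yet the protocol recognises a follow-up contact that produces no PSA and lets that contact extend event-free time. For a man whose last contacts are all by telephone, the interval between his last PSA and his last contact counts as relapse-free although no relapse could have been recorded in it. He stays in the Kaplan-Meier denominator and cannot enter the numerator, so the estimate moves in the favourable direction.

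A PSA deferred in mid-course and followed by a later draw does much less harm. The later draw can still show the rise, and the relapse is simply dated later. The inflation comes from men with no further PSA before the analysis.

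**Working it through.** **The plan's own figures.** No sample size, power or precision is stated for PSA relapse-free survival. The only operating characteristics are for the toxicity rule (12 or more of 40). The exact binomial tail gives 1.2%, 8.7%, 28.5%, 55.9%, 79.5%, 92.9% and 98.2% at true rates from 0.15 to 0.45, within one point of the Section 14.0 table. That rule does not use PSA.

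**Inputs.**
- From the documents: 92% PSA relapse-free at 7 years with the earlier combined treatment (Section 3.0), visits at months 1, 3, 6, 12, 18, 24, 30 and 36, and 40 evaluable men.
- Assumed: a constant relapse hazard; 10%, 20% or 30% of men with telephone contact only at the end; their last PSA at month 12 or month 24; contact with every man to month 36; deferral unrelated to relapse.

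**Step 1: expected relapses.** Hazard = −ln(0.92)/7 = 0.0119 per year. S(36 months) = exp(−3 × 0.0119) = 96.5%. Expected relapses by month 36 in 40 men = 40 × 3.5% = 1.4.

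**Step 2: bias of censoring at last contact.** If every man is followed to relapse or month 36, the Kaplan-Meier value at month 36 is the proportion without a recorded relapse. Let a share f have their last PSA at month L. Their relapses after L go unrecorded, so

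estimate = S(36) + f × [S(L) − S(36)], and bias = f × [S(L) − S(36)].

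With the hazard above, S(12) = 98.8% and S(24) = 97.6%. The brackets are 2.33 points (L = 12) and 1.16 points (L = 24). For other assumed values of S(36), S(12) = S(36)^(1/3) and S(24) = S(36)^(2/3).

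| True S(36) | Last PSA | f = 10% | f = 20% | f = 30% |
|---|---|---|---|---|
| 96.5% | month 24 | 0.12 | 0.23 | 0.35 |
| 96.5% | month 12 | 0.23 | 0.47 | 0.70 |
| 90% | month 24 | 0.32 | 0.64 | 0.97 |
| 90% | month 12 | 0.65 | 1.31 | 1.96 |
| 85% | month 24 | 0.47 | 0.95 | 1.42 |
| 85% | month 12 | 0.97 | 1.95 | 2.92 |

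Entries are percentage points of upward bias. A simulation of 400,000 men per setting, with relapse read at the protocol visits, agrees to within about 0.05 points. In the same simulation, censoring at the last PSA recovers the true value to within about 0.05 points.

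**Step 3: one cohort of the planned size.** Take 40 men, with relapses recorded at months 24 and 36.
- Censoring at last contact: (39/40) × (38/39) = 95.0%.
- Censoring k telephone-only men at their month-24 PSA: (39/40) × [1 − 1/(39 − k)]. This gives 94.7% for k = 4, 94.4% for k = 8 and 93.9% for k = 12.

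**The case against.** The strongest reply is that the intended meaning is already clear. Section 12.1 says the endpoint rests on serial PSA, PSA is scheduled at every follow-up, and a deferred test is ordinarily one done later, so last follow-up may simply mean last PSA follow-up. That may be the intent, but it is not stated. Section 10.1 uses follow-up for a contact without PSA, and an analyst working from the text could properly use the contact date.

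A second reply is that long telephone-only runs are limited. The option applies only when a man cannot attend, and Section 13.1 allows removal, after review, of men who cannot keep to the schedule. This makes extreme cases less likely. However, Section 10.1 treats the telephone contact as sufficient, and Section 13.1 sets no censoring date. Replacement under Section 14.0 concerns only the one-year toxicity status.

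A third reply is that the effect is small, and this stands. The exact 95% interval for 2 relapses in 40 men is 0.6% to 16.9%, far wider than any bias in the table.

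Two stronger readings are tempting, and the documents support neither.
- **A large distortion.** One missed relapse is 1/40 = 2.5 points against 1.4 expected relapses, so a reader might infer that most of the signal could be hidden. That would need about 70% of all relapses (1/1.4) to fall in the unobserved time of a minority of men. If 10 of 40 men had their last PSA at month 18, the bias at the hazard above is 0.25 × (98.2% − 96.5%), about 0.4 points. The other 30 men would be expected to show about 30 × 1.8% = 0.53 relapses after month 18.
- **Masking by treatment after biopsy.** Section 10.1 says "A repeat prostate biopsy will be completed between months 24 and 36 for pathologic response assessment", within the PSA follow-up period. A reader might infer that men treated after a positive biopsy are misclassified as relapse-free. The documents describe no treatment after biopsy, give no frequency, and take the relapse definition from an external consensus that cannot be checked here. How cancer treatment started before PSA relapse is handled is an open question, not a demonstrated error.

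**Conclusion.** The point holds as a minor one. Sections 10.1, 12.1 and 14.0 together allow event-free time to accrue without a PSA, and nothing elsewhere in the protocol corrects this. The bias is upward and confined to men whose final contacts lack a PSA. It is about 0.1 to 0.7 points at a true 36-month value of 96.5%, and at most about 2 points at 90% and 3 points at 85%.

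These sizes rest on the assumed constant hazard, the assumed 10% to 30% of men without a late PSA, and deferral unrelated to relapse. The documents give no deferral rate. The endpoint is secondary and descriptive, with no threshold or decision attached.

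**What to change.** In Sections 12.1 and 14.0, keep the present start date and relapse definition. State that in men without relapse the time ends at the date of the last PSA measurement, and that they are censored there in the Kaplan-Meier analysis. Report the number of men whose last contact had no PSA, so that readers can judge how much late follow-up is missing. If deferral turns out to be related to relapse, this censoring would no longer remove the bias fully, and the reported count is what would alert a reader to that.

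The sponsor should also say how the analysis treats cancer treatment started before PSA relapse. This is a request for clarification, with no particular rule proposed.

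The cost is a sentence or two in each section and one count in the report. PSA dates come with the PSA data already collected under Section 16.1. The visit schedule, sample size and toxicity rule do not change. The reported estimate may be slightly lower, and its interval slightly wider at late times.

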13.1 CRITERIA FOR REMOVAL FROM STUDY

The study subject will be removed from the study for any of the following reasons after review by the PI:

- 1) A change in patient's medical status unrelated to study treatment results in patient unable to comply with protocol
- 2) Patient is unable to meet dosimetric constraints in Section 9
- 3) Patient is unable to comply with followup schedule.
- 4) Patient request.
- 5) If ineligible for protocol as designated by Section 6, the patient will be removed.

14.0 BIOSTATISTICS

The primary objective is to assess the toxicity of hypofractionated radiation therapy in combination with brachytherapy for the treatment of intermediate risk prostate cancer. To set up a decision rule we will focus on the CTCAE v 4.0 (see appendix) grade 2 or higher GU toxicity observed at the 1-year follow-up time (+/- 4 weeks). We will enroll 40 evaluable patients, and if 12 or more patients have a CTCAE v4.0 grade 2 or higher toxicity at 1 year, this treatment will be deemed too toxic and the study will be stopped. Otherwise it will be declared safe. This decision rule has the following probabilities of declaring treatment unsafe

True toxicity rate	0.15	0.20	0.25	0.30	0.35	0.40	0.45
Probability of declaring unsafe	1%	8%	28%	56%	79%	92.9%	98.2%

Patients who withdraw, die due to reasons other than toxicity, or fail to provide the 1-year CTCAE v4.0 GU toxicity status will be replaced by new patients. To this end we may need to enroll an additional 4 patients (10%).

For the secondary objectives, all toxicities will be tabulated by type and grade. Post-treatment PSA values will be summarized numerically and graphically. Time to PSA relapse will be analyzed by Kaplan-Meier estimation. The pathologic response rates at 24-36 months will be calculated as sample proportion based on the available patients and confidence intervals will be provided. Erectile function evaluated by IIEF will be summarized by descriptive statistics.

It is expected that it will take approximately 3 years to accrue the total of 45 patients.

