LDR brachytherapy combined with conventional external beam radiotherapy for patients with intermediate risk prostate cancer addresses not only a need for dose escalation but also addresses concerns of dose coverage of extracapsular disease extension and is an accepted standard of care approach for intermediate risk disease (www.nccn.org). Long term outcomes using either LDR brachytherapy have been reported.^{12, 13, 15} We recently reported 7-year PSA relapse-free survival of 92% for patients with intermediate risk prostate cancer treated with prostate brachytherapy combined with 50.4Gy of external beam radiotherapy.¹⁴ With regards to toxicity, acute and late grade 3 or higher GU toxicity was noted in 2.3% and 3.1% respectively. Grade 2 late GU and GI toxicity were 21% and 4% respectively.

Although hypofractionated regimens for the definitive treatment of prostate cancer are considered part of a standard approach, the integration of a hypofractionated approach combined with brachytherapy has not yet been studied. To date, two ongoing studies are examining this in a Phase I setting (www.clinicaltrials.gov). The purpose of this study is to establish the toxicity associated with brachytherapy combined with hypofractionated radiation therapy.

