11.1 TOXICITIES/SIDE EFFECTS

The toxicities associated with radiation therapy to the prostate can be classified as either early (occurring within 90 days of treatment) or late (after 90 days). For the purpose of this study, the CTCAE v4.0 will be used as the primary endpoint to assess treatment-related toxicity. We expect that based on our prior studies^{14, 15}, 20% of patients of patients with have grade 2 or higher GU toxicity. The treatment will be considered to have significantly higher toxicity if ≥40% of patients in this study have ≥grade 2 at 12 months.

DEFINITIONS:

1. Adverse Event (AE)
 - a. An AE is defined by the GCP (Guide to Good Clinical Practice) as any undesirable experience occurring to a subject during a clinical trial, whether or not it is considered related to the investigational product(s).
2. Serious Adverse Event (SAE)
 - a. An SAE is an adverse experience that:
 - i. Is fatal or life-threatening
 - ii. Is disabling
 - iii. Results in hospitalization or prolongation of hospitalization
 - iv. Results in a congenital anomaly or occurrence of malignancy
 - v. Any urinary or rectal toxicity that is grade 3 or higher
3. Unexpected Adverse Event (UAE)
 - a. A UAE is an experience not previously reported (in nature, severity, or incidence) in the current Investigator's Brochure or general investigational plan.

Toxicities associated with radiation treatment include increased urinary frequency, urgency, weak stream, and nocturia. Other toxicities that may be related to radiation are fatigue, dysuria, hematuria, erectile dysfunction, urinary obstruction (due to edema or stricture), proctitis, bowel

injury or secondary cancers. Urinary, rectal, and erectile toxicities will be measured using IPSS, CTCAE v 4.0, and EPIC validated instruments (appendix).

The probability of severe (grade 3 or higher) urinary or rectal toxicity is expected to be $\leq 5\%$ which is currently observed rate of severe toxicity reported using standard combined brachytherapy and conventionally fractionated external beam radiation at MSKCC.¹⁴

To insure that unexpected significant toxicity is identified as early as possible with this treatment, we will observe the first 6 patients for a minimum of 3 months before enrolling any additional patients. If more than one patient has a grade 3 toxicity, we will wait 12 months before resuming accrual. If 4 or more patients of the first 6 patients have grade 3 or higher toxicity at 3 months we will terminate the study.

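### The safe verdict counts only GU toxicity present at month 12, while the 20% rate behind it has no stated time point and is not reconciled with the late rates in section 3.0

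*Combined protocol and SAP*

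**What the plan says.** Section 14.0 rests the decision on "grade 2 or higher GU toxicity observed at the 1-year follow-up time (+/- 4 weeks"). It sets the size, "We will enroll 40 evaluable patients", and the cut-off: "if 12 or more patients have a CTCAE v4.0 grade 2 or higher toxicity at 1 year, this treatment will be deemed too toxic". Any smaller count leads to a verdict of safe. Patients without a 1-year status are replaced. Toxicity at other visits is tabulated by type and grade, and the only confidence intervals planned in that section are for the biopsy response rates. Sections 2.1, 4.2 and 12.1 also place the primary assessment at 12 months.

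Section 11.1 calls toxicity early within 90 days of treatment and "late (after 90 days") from then on. It expects that "20% of patients of patients with have grade 2 or higher GU toxicity", citing references 14 and 15 and giving no time point. It then places the unacceptable level at 40% or more, at 12 months.

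Section 3.0 describes the centre's earlier series of brachytherapy plus 50.4 Gy external beam (reference 14): "acute and late grade 3 or higher GU toxicity was noted in 2.3% and 3.1% respectively", and "Grade 2 late GU and GI toxicity were 21% and 4% respectively". Neither sentence gives a time of assessment. The visit table in section 10.1 has CTCAE grading at months 1, 3 and 6, then every 6 months to month 36.

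**The concern.** The primary objective is late urinary toxicity, and late by the protocol's own definition covers everything from day 90 on. The verdict sees one visit. A grade 3 event at month 6 that is grade 1 by month 12, or a stricture first found at month 18, leaves that patient counted as free of toxicity in the 12-of-40 tally. Neither event enters any planned estimate with a confidence interval.

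This matters most when the result is compared with history. If the historical rates count late events whenever they occurred, a treatment with the same late toxicity as the old one would tend to look better than the old one, simply because it was read at a single visit. The 20% also fixes the column of the section 14.0 table that serves as the false-alarm rate, so its meaning and its value both need to be clear.

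**Working it through.** **Inputs.** n = 40 and cut-off 12 (section 14.0). Expected rate 20%, and unacceptable rate 40% at 12 months (section 11.1). Historical late GU toxicity 21% grade 2 and 3.1% grade 3 or higher (section 3.0).

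**Step 1: reproduce the plan's table.** P(unsafe) = P(X ≥ 12), X ~ Binomial(40, p), that is, the sum over k = 12 to 40 of C(40,k) p^k (1−p)^(40−k).

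| p | Printed | Recomputed |
|---|---|---|
| 0.15 | 1% | 1.2% |
| 0.20 | 8% | 8.75% |
| 0.25 | 28% | 28.5% |
| 0.30 | 56% | 55.9% |
| 0.35 | 79% | 79.5% |
| 0.40 | 92.9% | 92.9% |
| 0.45 | 98.2% | 98.2% |

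The table is right to within 1 point.

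**Step 2: what p must be.** The rule counts patients with grade 2+ at the 1-year visit, so p is the month-12 prevalence. The 40% limit is stated on that scale. The 20% is not tied to any scale.

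**Step 3: direction, if 20% is cumulative.** Let C be the proportion of patients with any late grade 2+ GU event over a period that includes month 12. Let f be the share of those patients who are at grade 2+ at the month-12 visit. Then p = C × f with f ≤ 1, so p cannot exceed C, and P(unsafe) cannot exceed its value at C.

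**Step 4: size, by assumption only.** The documents do not give f. With C = 20% and f = 0.75, p = 0.20 × 0.75 = 0.15 and P(unsafe) is 1.2%, against 8.75% at f = 1. As a hypothetical, take C = 40% on the cumulative scale (this is not the limit in section 11.1):

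| f | p = 0.40 × f | P(unsafe) |
|---|---|---|
| 1.0 | 0.40 | 92.9% |
| 0.9 | 0.36 | 83.0% |
| 0.8 | 0.32 | 66.4% |
| 0.6 | 0.24 | 23.6% |
| 0.5 | 0.20 | 8.75% |

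**Step 5: 20% against section 3.0.** If the 21% is grade 2 only, grade 2 or higher is 21% + 3.1% = 24.1%. If the 21% already includes higher grades, it is 21%. Taking each as the month-12 rate:

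| Rate | P(unsafe) |
|---|---|
| 20% | 8.75% |
| 21% | 11.7% |
| 24.1% | 24.1% (the equality is a coincidence) |

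**Step 6: the two together.** Steps 4 and 5 pull in opposite directions. With C = 24.1% and f = 0.8, p = 0.193 and P(unsafe) is 7.0%, close to the 8.75% at 20%. The two would cancel exactly at f = 0.20/0.241 = 0.83. Nothing in the documents says whether f is near that value.

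**The case against.** The 12-month landmark is deliberate and the same in every section that mentions it, and any fixed landmark leaves out later events. That stands, and the landmark should stay. Several stronger readings are tempting but are not supported.

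- **That the benchmark is documented as an any-time rate.** It is not. In section 3.0 the 7 years belongs to PSA relapse-free survival, not to toxicity. The any-time reading is inferred from the word late, the missing time point and the 90-day definition. If 20% is a 12-month rate, the mismatch disappears.
- **That the rule falls short of its 92.9% chance of catching a 40% rate.** Section 11.1 states 40% at 12 months, so 92.9% holds on the protocol's own scale. The lower figures in step 4 apply only to a cumulative 40% with an assumed f.
- **That section 3.0 shows late toxicity resolving before month 12.** The urinary bother described there rose at 1 month, which is early toxicity. It was patient-reported after external beam alone, and its decline is dated to 2 years. It gives no value for f.
- **That events at other visits are ignored.** They are graded to month 36 and tabulated. Section 11.1 makes grade 3 or higher urinary toxicity an SAE, with a review that may modify or end the study, and it adds a 3-month look at the first 6 patients. None of this enters the 12-of-40 verdict, which is the narrower point made here.
- **That 20% is wrong.** It cites a second study (reference 15) whose rate is not shown, and 24.1% assumes exclusive grades. It is unreconciled, not disproved.

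**Conclusion.** The point holds in a limited form. From the text alone, the verdict of safe reflects grade 2+ GU toxicity at one visit. Late events that resolve earlier or arise later do not enter it, and no planned toxicity estimate with an interval covers them.

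By inference, the historical rates are cumulative. If so, the comparison can only lean towards safe, by an amount that depends on a persistence fraction the documents do not give. The figures in step 4 show sensitivity and are not an estimate of bias.

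Separately, the 20% is not reconciled with section 3.0. If the month-12 rate were 24.1%, the rule would declare the treatment unsafe 24.1% of the time, not 8.75%, so this error runs the other way. The net direction is unknown until the sponsor says what the 20% measures. The binomial table and the 92.9% at a 12-month rate of 40% are correct.

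**What to change.** 1. Section 14.0: keep the 12-of-40 rule as the primary month-12 decision, and replace the word safe with acceptable 12-month GU toxicity.
2. Section 14.0, secondary analyses: add the cumulative incidence of first grade 2+ and of first grade 3+ GU toxicity after day 90, through months 12 and 36, with 95% CIs, from the visits already scheduled. Say how the month-3 visit is classed, since its 4-week window can fall on either side of day 90.
3. Use that estimate, not the month-12 count, for comparison with prior late rates, over the closest matching follow-up, and state any remaining difference in follow-up.
4. Section 11.1: say whether 20% is a 12-month or an any-time rate, show how references 14 and 15 lead to it, and reconcile it with 21% and 3.1%.

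The cost is protocol wording and one more analysis of data already collected, with no change to sample size, visits or cut-off. The conclusion becomes narrower, and the reported late rate will be equal to or higher than the month-12 figure.
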